### **12.1.3. Secondary Endpoint**

The secondary endpoint is the rate of moderate or greater paravalvular aortic regurgitation (based on review by an independent core lab) at 1 year. To control for experiment-wise type I error, testing for the secondary endpoint will be conducted only if the null hypotheses for the primary safety and the primary analysis of the primary effectiveness endpoints are rejected. That is, non-inferiority must be shown for the primary safety endpoint and the primary effectiveness endpoint for testing to be conducted for the secondary endpoint.

#### 12.1.3.1. Statistical Hypothesis for the Secondary Endpoint

The statistical hypothesis is that the secondary endpoint of moderate or greater paravalvular aortic regurgitation rate at 1 year (based on review by an independent core lab) for the Lotus Valve is superior to that for the CoreValve group.

The null and alternative hypotheses for the secondary endpoint are as follows:

$$H_0: P_{AR\_Lotus} = P_{AR\_Control}$$

$$H_1: P_{AR\_Lotus} \neq P_{AR\_Control}$$

where  $P_{AR\_Lotus}$  and  $P_{AR\_Control}$  correspond to the rates of moderate or greater paravalvular aortic regurgitation at 1 year for the Lotus Valve group (test) and the CoreValve group (control), respectively.

A chi-square test will be used to test the two-sided hypothesis of superiority between the rates of the two treatment groups, as described in the Statistical Analysis Plan. If the  $P$  value from the chi-square test is  $<0.05$  and the rate of the Lotus Valve group is less than the rate of the CoreValve group, the rate of moderate or greater paravalvular aortic regurgitation for the Lotus Valve group will be concluded to be superior to that of the CoreValve group.

#### 12.1.3.2. Sample Size Parameters for the Secondary Endpoint

The sample size calculation for the secondary endpoint (moderate/severe paravalvular aortic regurgitation rate at 1 year) is based on the following assumptions.

- Expected Lotus Valve (test) rate  $P_{AR\_Lotus} = 1.1\%$
- Expected CoreValve (control) rate  $P_{AR\_Control} = 5.3\%$
- Test significance level ( $\alpha$ ) = 0.05 (2-sided)
- Test : Control ratio = 2:1
- Expected rate of attrition = 25%

Given enrollment of 912 subjects (608 Lotus Valve, 304 CoreValve) and 25% attrition, there is approximately 86% power to show superiority with the given expected rates.

#### 12.1.3.3. Statistical Methods – Secondary Endpoint

Procedures similar to that described in Section 12.1.1.3 and discussed in the Statistical Analysis Plan will be applied to analysis of the secondary endpoint.

#### **12.1.4. Baseline Comparability**

Baseline data will be summarized by treatment group for the randomized subjects and separately for subjects in the roll-in (with the 23 mm, 25 mm, or 27 mm Lotus Valve), Lotus 21 mm Nested Registry, LOTUS Edge Nested Registry, roll-in with the 29 mm LOTUS Edge Valve, LOTUS Edge 29 mm Nested Registry, and U.S. Continued Access Study cohorts. Subject demographics, clinical and neurological history, risk factors, and preprocedure characteristics will be summarized using descriptive statistics (e.g., mean, standard deviation,  $n$ , minimum, maximum) for continuous variables and frequency tables or proportions for discrete variables. Treatments for the randomized subjects will be compared with a chi-square or Fisher exact test for discrete variables and a Student  $t$ -test for continuous variables. Treatment differences for the randomized subjects and their 95% confidence intervals will be presented. Procedural characteristics will be summarized similarly. No formal statistical testing will be done for the roll-in (with the 23 mm, 25 mm, or 27 mm Lotus Valve), Lotus

21 mm Nested Registry, LOTUS Edge Nested Registry, roll-in with the 29 mm LOTUS Edge Valve, LOTUS Edge 29 mm Nested Registry, or U.S. Continued Access Study subjects.

#### **12.1.5. Post-procedure Measurements**

Post-procedure information will be collected at regularly scheduled follow-up examinations as detailed in the clinical study schedule (Table 11.1-1) and will be summarized using descriptive statistics for continuous variables (e.g., mean, standard deviation, n, minimum, maximum) and frequency tables or proportions for discrete variables. Estimates will be reported by treatment group and, for randomized subjects, differences between treatment groups and their 95% confidence intervals will be presented. Treatments for the randomized subjects will be compared with the chi-square or Fisher exact test for discrete variables and the Student t-test for continuous variables. No inferences are planned on the additional measurements and, therefore, alpha-adjustments for multiple comparisons will not be used. The Kaplan-Meier product-limit method will be used to estimate rates for time-to-event endpoints and treatment groups will be compared using the Log-rank and Wilcoxon tests. Adverse event and SAE rates will be reported. No formal statistical testing will be done for the roll-in (with the 23 mm, 25 mm, or 27 mm Lotus Valve), Lotus 21 mm Nested Registry, LOTUS Edge Nested Registry, roll-in with the 29 mm LOTUS Edge Valve, LOTUS Edge 29 mm Nested Registry, or U.S. Continued Access Study subjects.

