  - Grade of aortic valve regurgitation: paravalvular, central and combined; the overall distribution of paravalvular aortic regurgitation (none, trace/trivial, mild, moderate, severe) will be determined as well as the percentage of subjects who have moderate or severe paravalvular regurgitation and the percentage of subjects who have mild, moderate or severe paravalvular regurgitation
- Clinical procedural success (30 days), defined as implantation of the study device in the absence of death, disabling stroke, major vascular complications, and life-threatening or major bleeding
- Procedural success (30 days), defined as absence of procedural mortality, correct positioning of a single transcatheter valve into the proper anatomical location, intended performance of the study device (effective orifice area [EOA]  $>0.9 \text{ cm}^2$  for BSA  $<1.6 \text{ m}^2$  and EOA  $>1.1 \text{ cm}^2$  for BSA  $\geq 1.6 \text{ m}^2$  plus either a mean aortic valve gradient  $<20 \text{ mm Hg}$  or a peak velocity  $<3 \text{ m/sec}$ , and no moderate or severe prosthetic valve aortic regurgitation) plus no serious adverse events at 30 days
- Additional indications of prosthetic aortic valve performance as measured by transthoracic echocardiography (TTE; see **Note 5** below) and assessed by an independent core laboratory, including effective orifice area, mean and peak aortic gradients, peak aortic velocity, and grade of aortic regurgitation (see **Note 6** below).
- Modified device success (30 days), reported for subjects randomized and implanted with an assigned study device and defined as follows: absence of mortality with the originally implanted transcatheter valve in the proper anatomical location, no additional aortic valve procedures, and with the intended performance of the prosthetic valve (either a mean aortic valve gradient  $<20 \text{ mm Hg}$  or a peak velocity  $<3 \text{ m/sec}$  with no moderate or severe prosthetic valve aortic regurgitation)
- Functional status as evaluated by the following:
  - 5-m gait speed test (at 1 year compared to baseline)
  - New York Heart Association (NYHA) classification
- Neurological status (see **Note 7** below) as determined by the following:
  - Neurological physical exam by a neurologist, neurology fellow, neurology physician assistant, or neurology nurse practitioner at discharge and 1 year
  - National Institutes of Health Stroke Scale (NIHSS) at discharge and 1 year

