- Modified Rankin Scale (mRS) at all time points
- Health status as evaluated by Kansas City Cardiomyopathy and SF-12 Quality of Life (QOL) questionnaires at baseline; 1 and 6 months; and 1, 3, and 5 years
- Resource utilization associated with the procedure and/or follow-up.

Additionally, assessment of leaflet thickening and mobility using 4D CT will be carried out at 30 days and 1 year post index procedure for subjects in the CT Imaging Substudy of the U.S. Continued Access Study. The CT scans will be evaluated by an independent CT Core Laboratory and should be blinded to local investigators for cardiac valve findings (local reading should be only for non-cardiac valve findings such as unexpected lung pathology; see Section 11.10.1 for additional information).

**Note 1:** The most current VARC definitions and endpoints available at the beginning of the trial were used.

**Note 2:** The VARC-2 safety composite at 30 days includes all-cause mortality, all stroke (disabling and non-disabling), life-threatening bleeding, acute kidney injury (Stage 2 or 3), coronary artery obstruction requiring intervention, major vascular complication, and repeat procedure for valve-related dysfunction. The VARC-2 time-related valve safety composite includes structural valve deterioration (valve-related dysfunction requiring repeat procedure [TAVR or SAVR]), prosthetic valve endocarditis, prosthetic valve thrombosis, thromboembolic events (e.g., stroke), and VARC bleeding (unless clearly unrelated to valve therapy based on investigator assessment)

**Note 3:** Clinical indications for permanent pacemaker implantation are outlined in the ACCF/AHA/HRS Guidelines for Device-Based Therapy of Cardiac Rhythm Abnormalities. Permanent pacemaker implantation should generally be performed only for accepted Class I indications.

**Note 4:** For the Lotus Valve System, repositioning may be achieved with partial or full resheathing of the valve; the proportion of subjects with partial valve resheathing and full valve resheathing will be determined.

**Note 5:** At least 1 echocardiogram must be obtained before discharge or 7 days (whichever comes first); if multiple echocardiographic studies are performed prior to discharge and within 7 days of the procedure, the latest study performed will be used for analysis.

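### NYHA class and modified Rankin score are compared by tests that ignore their ordering and give no direction or single effect estimate

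*Combined protocol and SAP*

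**What the plan says.** Section 12.1.5 sets the tests for all post-procedure measures: the randomized arms "will be compared with the chi-square or Fisher exact test for discrete variables", with a Student t-test for continuous ones. It also promises estimates by arm and, for randomized subjects, between-arm differences with 95% CIs. The only Wilcoxon test it names is for time-to-event endpoints. It then limits the status of these comparisons: "No inferences are planned on the additional measurements and, therefore, alpha-adjustments for multiple comparisons will not be used".

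Section 7.2 lists three ordered outcomes among the additional measurements:
- "New York Heart Association (NYHA) classification";
- "Modified Rankin Scale (mRS) at all time points";
- PVR grade, for which "the overall distribution of paravalvular aortic regurgitation (none, trace/trivial, mild, moderate, severe) will be determined". The same bullet also plans the percentages with moderate or severe PVR and with mild, moderate or severe PVR.

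PVR is handled separately for confirmatory purposes. Section 12.1.3 states: "The secondary endpoint is the rate of moderate or greater paravalvular aortic regurgitation". Section 12.1.3.1 gives the test: "A chi-square test will be used to test the two-sided hypothesis of superiority between the rates of the two treatment groups". Section 12.1.3.2 plans on 1.1% versus 5.3%, with about 86% power.

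**The concern.** A Pearson chi-square or Fisher exact test on a two-by-k table asks whether the arms differ in any way at all. It spreads its sensitivity over k−1 degrees of freedom and treats NYHA I to IV as four unrelated labels. The clinical question for NYHA and mRS is whether one arm tends towards better grades, and a rank or row-mean-score test puts its sensitivity on that question.

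There is a second gap that needs no power assumption. Section 12.1.5 promises differences with confidence intervals, but a k-category chi-square has no single difference to report. Category-by-category differences could be listed, but the plan names no one number that says how far functional or neurological status differs between the valves. With no multiplicity control on these measures, an estimate with an interval is worth more to the reader than an omnibus P value.

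**Working it through.** **1. The plan's own figure.** Section 12.1.3.2: 608 and 304 subjects less 25% attrition give 456 and 228; rates 1.1% and 5.3%; two-sided 0.05.
- Pooled rate: (228×0.053 + 456×0.011)/684 = 0.025.
- Null SE: √[0.025×0.975×(1/228 + 1/456)] = 0.01266.
- Alternative SE: √[0.053×0.947/228 + 0.011×0.989/456] = 0.01562.
- Power: Φ[(0.042 − 1.96×0.01266)/0.01562] = Φ(1.10) = 86.4%.

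The stated 86% reproduces. The outcome has two categories, so there is no ordering to lose.

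**2. NYHA and mRS.** The documents give no expected distribution or effect for either, so every input except the sample size is an assumption.
- Sample size: 456 versus 228, borrowed from the PVR endpoint.
- Lotus NYHA I–IV: 45/40/13/2%.
- Lotus mRS 0–5 in survivors: 30/30/20/12/6/2%.
- Control: every cumulative odds of a worse grade multiplied by a common OR. For example, NYHA II or worse in Lotus is 0.55, odds 1.222; at OR 1.5 the control odds are 1.833, so class I falls from 45% to 35.3%.
- Tests: Pearson chi-square on the full table versus tie-corrected Wilcoxon, two-sided 5%, 40,000 simulated trials per cell. Both hold about 5% at OR 1.

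| Measure | OR | Chi-square | Rank test | Gain (points) |
|---|---|---|---|---|
| NYHA | 1.3 | 28% | 41% | 13 |
| NYHA | 1.4 | 45% | 61% | 16 |
| NYHA | 1.5 | 61% | 76% | 16 (unrounded) |
| NYHA | 1.8 | 92% | 97% | 5 |
| mRS | 1.3 | 25% | 44% | 19 |
| mRS | 1.4 | 40% | 64% | 24 |
| mRS | 1.5 | 57% | 80% | 23 |
| mRS | 1.8 | 90% | 98% | 8 |

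A different NYHA start (50/38/10/2%) gives a gain of 12 points at OR 1.3. Counting death as a seventh mRS category (25/30/20/12/6/2/5%) gives 24% versus 45% at OR 1.3 and 54% versus 80% at OR 1.5.

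Cross-check without simulation: a one-degree-of-freedom test with 80% power has noncentrality (1.96 + 0.84)² = 7.84. The same noncentrality spread over 4 df gives 60% power and over 6 df gives 52%. The six-level mRS table has 5 df, and its 57% at OR 1.5 lies between them.

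**3. PVR grade, where the sign can change.** The Lotus distribution is adapted from the 1-year column of Table 4.1-4 (82.2/3.1/14.7/0/0%) to 82/3.1/13.8/1.0/0.1%, so that moderate or greater is the planned 1.1%. Control is set to the planned 5.3%; the spread over its grades is assumed.

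| Control none/trace/mild/moderate/severe (%) | Chi-square | Rank test |
|---|---|---|
| 77.8/3.1/13.8/5.0/0.3 (difference only in moderate or greater) | 78% | 34% |
| 74/4/16.7/5.0/0.3 (some shift in lower grades) | 86% | 73% |
| 70/6/18.7/5.0/0.3 (larger shift) | 96% | 95% |

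Under a purely proportional shift the rank test wins at modest ORs (OR 1.5: 39% versus 55%). The planned 1.1% versus 5.3% corresponds to (0.053/0.947)/(0.011/0.989) = 5.0, where both tests are at 100%.

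**The case against.** The strongest reply is that nothing in the plan depends on these tests. Section 12.1.5 disclaims inference on the additional measurements, and they have no hypothesis and no power target. That stands and keeps the point minor. It does not dispose of it, because the same section still prescribes the tests and promises differences with intervals.

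Second, the protocol defers detail to a Statistical Analysis Plan, and the text available contains no separate SAP passage on ordinal measures. An ordered method there cannot be ruled out. If there is one, Section 12.1.5 needs only an aligning sentence.

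Third, the power figures rest on assumed distributions and a proportional shift. That is so; they show the order of the loss under that pattern, not a forecast.

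A reader might go further and infer that the plan loses power on the device's main expected benefit, reduced PVR. The documents do not support that. The benefit is tested as a binary secondary endpoint and as a component of the primary effectiveness composite. Section 7.2 also plans the mild-or-worse cut-point, where an effect beyond the rare moderate grades would show. Nor does it follow that a rank test should replace the planned PVR analysis, or that its only weakness is non-monotone differences. A difference confined to moderate or greater PVR is monotone, is the protocol's own secondary hypothesis, and is where the rank test does worst (34% versus 78%).

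**Conclusion.** The point holds for NYHA class and mRS as a minor improvement to descriptive analyses. Section 12.1.5 assigns them a test that ignores order and supplies neither a direction nor a single effect estimate; that much follows from the text alone. The cost in power is about 12 to 16 points for NYHA and 19 to 24 for mRS at odds ratios of 1.3 to 1.5 with 456 versus 228 subjects, and shrinks for larger effects. These sizes depend on assumed distributions, an assumed proportional shift and attrition borrowed from another endpoint. For full PVR grade the choice of test is a trade-off that can go either way. The sample size, the alpha allocation, both primary endpoints and the secondary endpoint are untouched.

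**What to change.** In Section 12.1.5 (and the SAP, if it is silent):
- Compare NYHA class and mRS between randomized arms by a Wilcoxon or Cochran–Mantel–Haenszel row-mean-score test, stratified by the randomized risk group (high or extreme). Report a common odds ratio or the probability of a better grade with its 95% CI, labelled descriptive.
- State how deaths before the visit enter these comparisons (survivors only, or death as the worst category). The estimate depends on it: 1-year mortality was 11.6% in the REPRISE II full cohort (Table 4.1-4).
- For PVR, keep the moderate-or-worse and mild-or-worse percentages with differences and 95% CIs. Add an ordered comparison of the full grade distribution only as a supplement.
- Keep chi-square or Fisher for binary and nominal measures.

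The cost is a few lines of text and slightly more programming. The statistical downside is lower sensitivity to a difference confined to one rare end category, which is why the PVR cut-points stay.

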--	---

**REPRISE III: REpositionable Percutaneous Replacement of Stenotic Aortic Valve through Implantation of Lotus™ Valve System – Randomized Clinical Evaluation**

measured by transthoracic echocardiography (TTE; see **Note 3** below) and assessed by an independent core laboratory, including effective orifice area, mean and peak aortic gradients, peak aortic velocity, and grade of aortic regurgitation

- Modified device success (30 days), reported for subjects randomized and implanted with an assigned study device and defined as follows: absence of mortality with the originally implanted transcatheter valve in the proper anatomical location, no additional aortic valve procedures, and with the intended performance of the prosthetic valve (either a mean aortic valve gradient <20 mm Hg or a peak velocity <3m/sec with no moderate or severe prosthetic valve aortic regurgitation)
- For subjects who received a permanent pacemaker related to the index procedure, results of pacemaker interrogation at 30 days and 1 year
- Functional status as evaluated by the following:
  - 5-m gait speed test (at 1 year compared to baseline)
  - New York Heart Association (NYHA) classification
- Neurological status (see **Note 4** below) as determined by the following:
  - Neurological physical exam at discharge and 1 year (conducted by a neurologist, neurology fellow, neurology physician assistant, or neurology nurse practitioner)
  - National Institutes of Health Stroke Scale (NIHSS) at discharge and 1 year
  - Modified Rankin Scale (mRS) at all time points
- Health status as evaluated by Kansas City Cardiomyopathy and SF-12 Quality of Life questionnaires at baseline; 1 and 6 months; and 1, 3, and 5 years

Additionally, assessment of leaflet mobility using 4D CT will be carried out at 30 days and 1 year for subjects in the CT Imaging Substudy of the U.S. Continued Access Study. The data will be evaluated by an independent CT core lab.

**Note 1:** The most current VARC definitions and endpoints available at the beginning of the trial were used.

**Note 2:** For the Lotus Valve (test), repositioning may be achieved with partial or full resheathing of the valve.

**Note 3:** At least 1 echocardiogram must be obtained before discharge or 7 days (whichever comes first); if multiple echocardiographic studies are performed prior to discharge and within 7 days of the procedure, the latest

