**Table 11.1-1: Study Event Schedule**

Assessment	Screening a	Baseline	Procedure	Within 1 Day Post-procedure	Prior to Discharge or 7 Days Post-Procedure	30 Days b (±7 Days) Office Visit	6 Months b (±30 Days) Office Visit	12 Months b (±30 Days) Office Visit	24–60 Months b [Annual] (±45 Days) Office Visit
------------	------------------------	----------	-----------	-----------------------------	---	---	---	--	--

rhythm strip should be obtained after BAV and before study valve insertion (12-lead ECG is not required during the procedure).

- f: Laboratory tests at baseline include CBC with platelets, albumin, serum creatinine, and cardiac enzymes. Cardiac enzymes (CK is required, CK-MB or troponin if CK is elevated) must be collected twice at intervals per standard of care within 6-24 hours post-procedure. Acute kidney injury (AKI) should be assessed through discharge/7 days based on the AKIN system.
- g: Consists of STS score, euroSCORE II (2011), and heart team assessment including an in-person evaluation by a center cardiac surgeon that must be confirmed by the CRC (which must include an experienced cardiac surgeon). In the United States, the Centers for Medicare and Medicaid Services require independent evaluations by 2 cardiac surgeons for reimbursement.
- h: Frailty, disability, and comorbidity risk assessments must be captured at screening: height, weight, cognitive function (Mini-Cognitive Assessment for Dementia), strength and balance (use of wheelchair, gait speed to walk 5 meters, number of falls in the past 6 months, maximal grip strength), and activities of daily living (Katz Index); at 1 year, gait speed to walk 5 meters must be assessed again.

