**Table 11.1-1: Study Event Schedule**

Assessment	Screening a	Baseline	Procedure	Within 1 Day Post-procedure	Prior to Discharge or 7 Days Post-Procedure	30 Days b (±7 Days) Office Visit	6 Months b (±30 Days) Office Visit	12 Months b (±30 Days) Office Visit	24–60 Months b [Annual] (±45 Days) Office Visit
------------	------------------------	----------	-----------	-----------------------------	---	---	---	--	--

Imaging Core Laboratory procedure guidelines (see study Manual of Operations). Results must be forwarded to the CT/X-Ray Core Laboratory for analysis. If additional imaging is performed (e.g., cardiac CT or MRI scan), data may be provided for analysis.

- o: Includes the Kansas City Cardiomyopathy and SF-12 QOL questionnaires. Baseline QOLs should be performed within 30 days prior to the index procedure.
- p: QOL survey at 36 and 60 months.
- q: Procedural cine-angiogram including final post-deployment aortogram of the ascending aorta must be done and sent to the CT/X-Ray Core Laboratory for analysis.
- r: For subjects who received a permanent pacemaker related to the index procedure, pacemaker dependence must be captured at the 30-day and 1-year visits via pacemaker interrogation. Pacemaker interrogation should also include assessment of the percentage of beats where the ventricles are paced.
- s: AEs and ADEs will be monitored and collected from the time of enrollment through 12-month follow-up. For subjects who do not receive the study device, AEs will be monitored through 1-year follow-up.
- t: Information on device deficiencies for the test and the control devices, as well as all SAEs, SADEs, UADEs, USADEs, and CEC events will be monitored and reported to Boston Scientific for all enrolled subjects from the time of enrollment through termination of the study. For subjects who do not receive a study device (test or control), the mentioned events will be monitored through 1 year post-index procedure. Please refer to Section 7.2 for a list of CEC events and Table 26.2-1 for definitions of these events, which specify data required for CEC adjudication. Complaint reporting of any device deficiencies for any commercially available products used should also be carried out using the manufacturer’s processes.

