### 11.5. *Baseline Assessments*

The following assessments must be completed within 30 days prior to the index procedure, unless otherwise specified below. The REPRISE III electronic eCRFs identify the specific data points to be collected.

- Confirmation of eligibility criteria
- Neurological physical examination, which must be performed by a neurologist, neurology fellow, neurology physician assistant, or neurology nurse practitioner (see Table 11.1-1); assessors should be independent (not involved with the care of study subjects).
- NIH Stroke Scale (NIHSS), which must be performed by a neurology professional or certified personnel (external certification); assessors should be independent (not involved with the care of study subjects)
- Modified Rankin Scale score, which must be performed by a neurology professional or certified personnel (external or internal certification); assessors should be independent (not involved with the care of study subjects)
- Laboratory tests
  - Complete blood count (CBC) with platelets
  - Albumin
  - Serum creatinine
  - Cardiac enzymes (CK is required, CKMB or troponin if CK is elevated)
- Quality Of Life (QOL) Surveys: Kansas City Cardiomyopathy and SF-12 QOL Questionnaires must be administered to the subject within 30 days prior to the procedure.

**Note:** In cases where a subject who has met the echocardiographic criteria for enrollment receives BAV prior to the index procedure and subsequently no longer meets the REPRISE III aortic valve pressure gradient or EOA criteria, the subject may still be enrolled based on the pre-BAV echocardiographic data. In such cases, the most recent echocardiogram done prior to the index procedure (even if after BAV) must be submitted to the Echocardiography Core Laboratory to be included in the baseline data.

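### Free improvement: KCCQ, SF-12, gait speed and LVEF are compared by a t-test with no baseline adjustment, so their descriptive confidence intervals are wider than they need to be

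*Combined protocol and SAP*

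**What the plan says.** Section 12.1.5 covers the information collected at scheduled follow-up visits. For continuous measures in the randomized arms it prescribes a t-test ("and the Student t-test for continuous variables") and adds that "differences between treatment groups and their 95% confidence intervals will be presented". It names no covariate and does not say whether the test is applied to the follow-up value or to the change from baseline. The same section states: "No inferences are planned on the additional measurements".

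An earlier value is required for each measure at issue:

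- **KCCQ and SF-12.** Section 7.2 schedules the "questionnaires at baseline; 1 and 6 months; and 1, 3, and 5 years". Section 11.5 requires that the "QOL Questionnaires must be administered to the subject within 30 days prior to the procedure", and Table 11.1-1, footnote o, gives the same window: "Baseline QOLs should be performed within 30 days prior to the index procedure".
- **Gait speed.** Footnote h of the table makes it a screening item and adds that "at 1 year, gait speed to walk 5 meters must be assessed again". The synopsis lists the measure as "5-m gait speed test (at 1 year compared to baseline".
- **LVEF, gradients and EOA.** Footnote i includes them in the echocardiographic assessment, and a screening echocardiogram is required before Case Review Committee (CRC) review.

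Section 12.3.4 plans multivariable modelling, but only for the two primary endpoints and the secondary endpoint. Section 12.1.4 compares baseline characteristics between arms without using them in any later comparison of these measures.

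**The concern.** A t-test on the follow-up value leaves in the error term all the between-patient variation that the baseline value could explain. Any chance difference in baseline between the arms also stays in the estimate. A t-test on change, which the gait-speed wording suggests, does use the baseline but gives it a fixed coefficient of 1. If the correlation is below 0.5, that is less precise than ignoring the baseline altogether.

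These comparisons are the trial's randomized evidence on health status and function. Section 12.1.6 repeats comparisons on additional endpoints within subgroups, where intervals are wider. What is at stake is the width of those intervals and the nominal P values beside them.

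**Working it through.** **The plan's own figures.** The documents give no sample size, power or standard deviation assumption for KCCQ, SF-12, gait speed or LVEF, so there is no stated figure for these measures to reproduce. The numbers of patients used below come from the endpoint calculations. For the primary effectiveness endpoint (Section 12.1.2.2.1: 32% in both arms, margin 9.5%, one-sided 0.025, 2:1, 80% power), the Farrington-Manning calculation gives 819 as the smallest total, with power 80.1%. This matches the plan. With 912 randomized:

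- 10% attrition leaves 912 × 0.90 = 821 (547 and 274).
- The 25% attrition assumed for the 1-year echocardiographic endpoint (Section 12.1.3.2) leaves 912 × 0.75 = 684 (456 and 228).

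**Relative precision.** Let r be the within-arm correlation between baseline and follow-up, with equal variances at the two times and a common slope in both arms. The variance of the treatment difference, relative to a t-test on the follow-up value, is:

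- t-test on follow-up value: 1
- t-test on change: 2(1 − r)
- ANCOVA: 1 − r²

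ANCOVA therefore shortens the CI by 1 − √(1 − r²) relative to the t-test on the follow-up value. Relative to ANCOVA, the change score has variance 2(1 − r)/(1 − r²).

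| r (assumed) | ANCOVA variance | Change-score variance | CI reduction, ANCOVA vs follow-up value | Extra variance, change vs ANCOVA |
|---|---|---|---|---|
| 0.1 | 0.99 | 1.80 | 0.5% | 82% |
| 0.3 | 0.91 | 1.40 | 4.6% | 54% |
| 0.5 | 0.75 | 1.00 | 13.4% | 33% |
| 0.6 | 0.64 | 0.80 | 20.0% | 25% |
| 0.7 | 0.51 | 0.60 | 28.6% | 18% |

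**In SD units.** The unadjusted 95% half-width is 1.96 × √(1/n₁ + 1/n₂).

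- 547 and 274: 1.96 × 0.0740 = 0.145 SD. With ANCOVA: 0.138 (r = 0.3), 0.126 (0.5), 0.116 (0.6).
- 456 and 228: 1.96 × 0.0811 = 0.159 SD. With ANCOVA: 0.152, 0.138 and 0.127.

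The 10% figure belongs to a composite in which a death counts as an outcome. Patients who have died cannot contribute a 1-year questionnaire or walk, so the second line is probably nearer the truth. The percentage reductions do not depend on which is used.

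**Gradients and EOA.** Baseline here is the native valve, restricted by inclusion criterion IC1 (valve area at most 1.0 cm² or index at most 0.6 cm²/m², with mean gradient at least 40 mm Hg or jet velocity at least 4.0 m/s). Follow-up measures the prosthesis. In the REPRISE II full cohort the 1-year mean gradient was 12.49 mm Hg with SD 5.35 (Table 4.1-4). With 684 patients the unadjusted half-width is 0.159 × 5.35 = 0.85 mm Hg. ANCOVA leaves it at 0.85 at r = 0.1 and reduces it to 0.81 at r = 0.3. A correlation near zero is plausible here, so little should be expected.

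**Timing of the baseline.** Gait speed and the screening echocardiogram precede CRC approval, and randomization follows that approval (Sections 8.2 and 11.4). The KCCQ and SF-12 window is instead tied to the procedure, and Section 8.2 allows the procedure up to 30 days after randomization. A questionnaire inside its permitted window may therefore have been completed after randomization.

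**The case against.** The strongest case on the other side is that nothing here is wrong. Under randomization an unadjusted t-test is valid and unbiased. The measures are outside the testing hierarchy of Section 12.1, Section 12.3.1 describes them as having no statistical hypothesis behind them, and Section 12.1.5 plans no inference on them. Section 12.1.4 will show any imbalance in the baseline measures it reports. All of that stands, and it is why this is a free improvement and not a defect.

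Three stronger readings are tempting, and the documents do not support them:

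- **That the trial is under-sized.** A reader might turn 1/(1 − r²) into 10%, 33% or 56% more patients at r = 0.3, 0.5 and 0.6. That is a fair way to express precision, but no sample size in the plan rests on these measures, so none is wasted or missing.
- **That every echocardiographic measure would benefit.** The native-valve baseline makes that doubtful for gradients and EOA, as shown above.
- **That the plan certainly ignores baseline.** Section 12.1.5 is silent on value versus change, and the gait-speed wording points to change. ANCOVA is at least as precise under either reading, but the loss differs. The protocol also refers to a separate Statistical Analysis Plan (Section 12.2). If that document already names a model, Section 12.1.5 should be aligned with it.

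The objection is also right that a pre-randomization KCCQ or SF-12 value is not guaranteed. The fix needs a rule for that case.

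**Conclusion.** The point holds as an efficiency improvement for KCCQ, SF-12, gait speed and LVEF. Against a t-test on the follow-up value, the available reduction in CI width is about 5%, 13% and 20% at r = 0.3, 0.5 and 0.6. Against a t-test on change, ANCOVA removes extra variance of 54%, 33% and 25% at the same correlations. These sizes rest entirely on assumed correlations and on the equal-variance, common-slope approximation. That ANCOVA is at least as precise as either t-test, apart from a negligible loss of degrees of freedom, does not depend on the value of r. Only the reported differences, their intervals and the nominal P values would change.

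**What to change.** In Section 12.1.5, and in the Statistical Analysis Plan to match:

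- Compare KCCQ, SF-12, 5-m gait speed and LVEF between randomized arms by ANCOVA at each scheduled visit. The follow-up value is the outcome; treatment, baseline value and the high/extreme risk stratum used in randomization are covariates. Report the adjusted difference and its 95% CI.
- Keep the t-test for continuous measures with no baseline value. Treat adjustment as optional for gradients and EOA.
- For KCCQ and SF-12, adjust only for a value obtained before randomization. Treat a baseline obtained only afterwards as missing, and replace a missing covariate by its simple mean over both arms so that no patient with a follow-up value is dropped.
- For LVEF, name the screening echocardiogram as the covariate. After a valvuloplasty, footnote i of Table 11.1-1 brings a later, pre-procedure study into the baseline data, and that study could fall after randomization.

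The cost is wording. No visits, measurements or patients are added. Section 12.3.5 already provides the route: an amended Statistical Analysis Plan approved before the analyses are performed. The questionnaire completion date must be compared with the randomization date. Where many baselines fall after randomization, the gain for KCCQ and SF-12 shrinks, but validity is unaffected.
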